6.13.3. Vital Signs, Weight, and ECG Evaluation

Change from baseline to Visit 7 in vital signs, body weight will be analyzed by the ANCOVA model with treatment as the fixed effect and baseline value as a covariate for between-group differences. Missing data will be imputed by LOCF method.

The numbers and percentages of patients with treatment-emergent abnormal, high, or low vital signs at any time during treatment or tapering period will be summarized and compared between treatment groups using Fisher's exact test.

A treatment-emergent abnormal result is defined as a change from normal at baseline to abnormal at any time during the treatment or tapering period. A treatment-emergent high result is defined as a change from a value less than or equal to the high limit at baseline to a value greater than the high limit at any time during the treatment or tapering period. A treatment-emergent low result is defined as a change from a value greater than or equal to the low limit at baseline to a value less than the low limit at any time during the treatment or tapering period.

By-patient listings of vital signs, body weight and ECG will be presented for all randomized patients.

6.13.4. Clinical Laboratory Evaluation

Change from baseline to Visit 7 in each of the laboratory tests (including the groups of hematology, clinical chemistry (including HbA1c and glucose), urinalysis) will be analyzed by the ANCOVA model with treatment as the fixed effect and baseline value as a covariate for between-group differences. Missing data will be imputed by LOCF method.

The numbers and percentages of patients with treatment-emergent abnormal, high, or low laboratory results at any time during treatment or tapering period will be summarized and compared between treatment groups using Fisher's exact test.

A treatment-emergent abnormal result is defined as a change from normal at baseline to abnormal at any time during the treatment or tapering period. A treatment-emergent high result is defined as a change from a value less than or equal to the high limit at baseline to a value greater than the high limit at any time during the treatment or tapering period. A treatment-emergent low result is defined as a change from a value greater than or equal to the low limit at baseline to a value less than the low limit at any time during the treatment or tapering period.

A lab listing for all randomized patients will be provided, including the actual measurement, abnormal result, and reference low or high limits.

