#### List of Attachments

# 4. Abbreviations and Definitions

Term	Definition
AE	adverse event: Any untoward medical occurrence in a patient or clinical investigation subject administered a pharmaceutical product that does not necessarily have a causal relationship with this treatment. An adverse event can, therefore, be any unfavorable and unintended sign (including an abnormal laboratory finding), symptom, or disease temporally associated with the use of a medicinal (investigational) product, whether or not related to the medicinal (investigational) product.
ALT	alanine aminotransferase
ANCOVA	analysis of covariance
AST	aspartate aminotransferase
audit	A systematic and independent examination of the trial-related activities and documents to determine whether the evaluated trial-related activities were conducted, and the data were recorded, analyzed, and accurately reported according to the protocol, applicable standard operating procedures (SOPs), good clinical practice (GCP), and the applicable regulatory requirement(s).
BDI-II	Beck Depression Inventory-II
BID	twice daily
blinding	A procedure in which one or more parties to the trial are kept unaware of the treatment assignment(s). Unless otherwise specified, blinding will remain in effect until final database lock.
	A single-blind study is one in which the investigator and/or his staff are aware of the treatment but the patient is not, or vice versa, or when the sponsor is aware of the treatment but the investigator and/his staff and the patient are not.
	A double-blind study is one in which neither the patient nor any of the investigator or sponsor staff who are involved in the treatment or clinical evaluation of the subjects are aware of the treatment received.
BOCF	baseline observation carried forward
BPI-SF	Brief Pain Inventory-Short Form
CGI-I	Clinical Global Impression of Improvement
CGI-S	Clinical Global Impression of Severity
CI	confidence interval
CIOMS	Council for International Organizations of Medical Sciences
complaint	A complaint is any written, electronic, or oral communication that alleges deficiencies related to the identity, quality, purity, durability, reliability, safety or effectiveness, or performance of a drug or drug delivery system.

Term	Definition
compliance	Adherence to all the trial-related requirements, good clinical practice (GCP) requirements, and the applicable regulatory requirements.
CrCL	creatinine clearance
C-SSRS	Columbia Suicide Severity Rating Scale

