- [19] Answered "yes" to either Question 4 (Active Suicidal Ideation with Some Intent to Act, Without Specific Plan) or Question 5 (Active Suicidal Ideation with Specific Plan and Intent) on the "Suicidal Ideation" portion of the Columbia-Suicide Severity Rating Scale (C–SSRS) or answered "yes" to any of the suicide-related behaviors (actual attempt, interrupted attempt, aborted attempt, preparatory act or behavior) on the "Suicidal Behavior" portion of the C–SSRS; and the ideation or behavior occurred within the past month
- [20] Have past history of psychiatric diseases, such as depression, anxiety disorder, eating disorder, etc., that required drug therapy in the past 1 year, or who are currently having complications of these diseases or any history of manic psychosis or bipolar disorder
- [21] Have MDD as determined using depression module of the Mini-International Neuropsychiatric Interview (MINI)
- [22] Have complications of diseases that are considered to affect the assessment of diabetic peripheral neuropathic pain. For example, nerve diseases with pain other than diabetic peripheral neuropathic pain (cervical spondylosis, carpal tunnel syndrome, spinal canal stenosis, and post-herpetic pain), pain diseases other than nerve diseases (collagen diseases, gout, chronic obstructive arteriosclerosis, and arthritis), and other pain at the site of evaluation (skin diseases and traumatic injury) are excluded.
- [23] Have neuropathic pain suspected to be caused by alcohol

- [24] Have past history of drug abuse or dependence (including alcohol dependence) in the past 1 year, or who are currently having complication, thereof
- [25] Considered unsuitable to participate in the study as judged by the investigator
- [26] Have been treated with a monoamine oxidase (MAO) inhibitor(s) within 14 days immediately prior to Visit 2. Patients who visited the investigator site 14 days prior to Visit 2, those who have been treated with MAO inhibitors(s), thereafter, are excluded
- [27] Have alanine aminotransferase (ALT) and aspartate aminotransferase (AST) at a level ≥100 U/L at Visit 1
- [28] Have total bilirubin at a level  $\geq 1.5$  mg/dL at Visit 1
- [29] Have creatinine clearance (CrCL), calculated by Cockroft-Gault, that is <1.0 mL/s (<60mL/min) at Visit 1
- [30] Have a white blood cell (WBC) value <2500/mm^3, neutrophils <1500/mm^3, or platelets <100×103/mm^3 on their hematology tests at Visit 1

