## 8.3.3. Patient Discontinuation from the Study

In addition, patients will be discontinued from the study in the following circumstances:

- Enrollment in any other clinical trial involving study drug or enrollment in any other type of medical research judged not to be scientifically or medically compatible with this study
- Investigator Decision
  - The investigator decides that the patient should be discontinued from the study

- If the patient, for any reason, requires treatment with another therapeutic agent that has been demonstrated to be effective for treatment of the study indication, discontinuation from the study occurs prior to introduction of the new agent
- Subject Decision
  - The patient requests to be withdrawn from the study
- Sponsor Decision
  - Lilly, Shionogi, or its designee stops the study or stops the patient's participation in the study for medical, safety, regulatory, or other reasons consistent with applicable laws, regulations, and GCP
- Adverse Event
  - If the investigator decides that the patient should be withdrawn because of an SAE or a clinically significant laboratory value, the study drug is to be discontinued and appropriate measures are to be taken. Lilly, Shionogi, or its designee is to be alerted immediately. Refer to Safety Evaluations Section 10.4.
- The patient experiences a clinically severe AE, in the opinion of the investigator, that would preclude further participation in the study, or the patient does not tolerate the planned dosages.
- The female patient is willing to become pregnant, or becomes pregnant. The male patient is willing to have a child.
- There is a significant protocol violation, as determined by the investigator or sponsor.
- The patient answers "yes" to either Question 4 (Active Suicidal Ideation with Some Intent to Act, Without Specific Plan) or Question 5 (Active Suicidal Ideation with Specific Plan and Intent) on the "Suicidal Ideation" portion of the C-SSRS during the study period, or answers "yes" to any of the suicide-related behaviors (actual attempt, interrupted attempt, aborted attempt, preparatory act or behavior) on the "Suicidal Behavior" portion of the C-SSRS.

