6.2. General Considerations

Statistical analysis of this study will be the responsibility of Eli Lilly. Analyses will be conducted using SAS 9.2 (or later).

Efficacy analyses will be conducted on the full analysis set (FAS), unless otherwise stated. The FAS includes all data from all randomized patients receiving at least 1 dose of the study drug according to the treatment the patients were assigned. When mean change from baseline to endpoint is assessed, data will be included in the analysis only if there is a baseline and a corresponding postbaseline measure.

Safety analyses will be conducted on the safety analysis set. This set includes all randomized patients who received at least 1 dose of study drug. Safety analyses will be based on the treatment the patients actually received.

Analyses based on the per-protocol set (PPS) will be performed to examine the robustness of the primary efficacy analysis. The PPS will be defined as a subset of patients in FAS who did not have major protocol deviations.

All tests of hypotheses will be considered statistically significant if the 2-sided p-value is <0.05 , unless otherwise stated. No adjustments for multiple comparisons will be made.

Any change to the data analysis methods described in the protocol will require an amendment ONLY if it changes a principal feature of the protocol. Any other change to the data analysis methods described in the protocol, and the justification for making the change, will be described in the SAP and clinical study report. Additional exploratory analyses of the data will be conducted as deemed appropriate.

Baseline value for a variable will be defined as the last non-missing value for this variable prior to or at randomization visit (Visit 2), unless otherwise specified.

The endpoint value for an efficacy variable is defined as the last non-missing post baseline value prior to or at Visit 6 (Week 12), unless otherwise stated.

The endpoint value for a safety variable is defined as the last non-missing post baseline value prior to or at Visit 7 (Week 13), unless otherwise stated.

In general, descriptive summary statistics will include:

- for categorical variables: number and percentage (with the percentage excluding the number missing in the denominator)
- for continuous variables: number, mean, median, standard deviation, minimum, and maximum.

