6.13.2. Adverse Events

An adverse event is any untoward medical event associated with the use of a drug in humans, whether or not it is considered related to a drug. Adverse events will be classified according to the Medical Dictionary for Regulatory Activities (MedDRA) and summarized by treatment group. TEAEs for treatment period will be defined as events that are newly reported or reported

to worsen in severity after the initiation of study drug through the treatment period. TEAEs for tapering period will be defined as events that are newly reported or reported to worsen in severity during the tapering period. Similarly, TEAEs for follow-up period will be defined as events that are newly reported or reported to worsen in severity during the follow-up period. The incidence of patients with at least one TEAE and the incidence of TEAEs by MedDRA preferred term and system organ class will be presented by treatment group. Fisher's exact test will be used for treatment comparison. These analyses will be summarized by treatment period, tapering period and follow-up period separately, and summarized for combined periods (treatment + tapering + follow-up). All the other analyses below will be summarized for combined periods only.

Treatment-Emergent Adverse Drug Reactions (ADR) will be also by summarized using MedDRA Preferred Term by treatment group. Here, Treatment-Emergent ADR means that TEAEs indicated by the investigator on the Case Report Form (CRF) to be possibly related to the study drug. Similarly, summaries of serious adverse event (SAE), AE leading to discontinuation will be provided separately.

The incidence of patients with TEAEs by maximum severity will be summarized by treatment group using MedDRA Preferred Term nested within System Organ Class.

An overview of AEs will be provided. This summary will include the number and percentage of patients who experienced a TEAE, death, SAE, ADRs, AE leading to discontinuation.

By-patient listings of TEAEs, and SAEs (including death) including the same event on several occasions will be presented. The listings will include both preferred term and the original term used by the investigators.

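### SAP 6.13.4 plans no by-arm laboratory count of how far ALT, AST or bilirubin rose, of both rising together, or of worsening from a raised ALT/AST baseline

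*SAP*

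**What the plan says.** SAP 6.13.4 plans three laboratory outputs:

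- an ANCOVA of change from baseline to Visit 7, with LOCF;
- by-arm numbers and percentages with a treatment-emergent abnormal, high or low result at any time in the treatment or tapering period, compared by Fisher's exact test;
- a by-patient listing of values and reference limits.

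Treatment-emergent high is "a change from a value less than or equal to the high limit at baseline to a value greater than the high limit". Treatment-emergent abnormal requires a normal baseline. Protocol 12.2.9 adds no liver-specific count.

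Other sections use multiples of ULN. Protocol 10.4.3 starts clinical and laboratory monitoring at ALT or AST above 3 times ULN or bilirubin above 2 times. Protocol 8.3.2 asks the investigator to consider stopping study drug in four situations:

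- ALT or AST above 8 times ULN;
- above 5 times for more than 2 weeks;
- above 3 times with bilirubin above 2 times or prothrombin time above 1.5 times;
- above 3 times with symptoms or eosinophilia.

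On entry, exclusion [27] reads "Have alanine aminotransferase (ALT) and aspartate aminotransferase (AST) at a level ≥100 U/L at Visit 1". Exclusion [28] bars total bilirubin of 1.5 mg/dL or more at Visit 1.

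**The concern.** The protocol treats the size of a liver test rise, and the combination of enzymes with bilirubin, as clinically meaningful. The planned by-arm laboratory tables record neither. They show only whether a patient who began within the limit later went outside it.

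From those tables a reader could not say how many patients per arm passed the protocol's own monitoring threshold or reached the levels at which stopping is considered. Patients who entered with a raised ALT or AST and got worse would be missing from the treatment-emergent count.

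Both documents make clinical laboratory tests part of the secondary safety comparison (Protocol 6.2, SAP 4.2). HbA1c and glucose are the named examples, so liver tests fall under the general wording only. By contrast, SAP 6.13.5 enumerates suicide-related events by graded category and arm.

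**Working it through.** **What the counting rule does.** Values are multiples of ULN.

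| Baseline to maximum | Counted as treatment-emergent high? |
|---|---|
| at or below 1, to 1.05 | yes |
| at or below 1, to 9 | yes, identically |
| 1.5 to 9 (9/1.5 = 6.0 times baseline) | no |
| 1.2 to 2.9 (2.9/1.2 = 2.42 times baseline) | no |
| ALT above 3 and bilirubin above 2, both from normal | once under each test, with no link |

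**Whether raised baselines occur.** The Study Schedule (Protocol Attachment 1) draws chemistry before treatment only at Visit 1. SAP 6.2 takes the last non-missing value up to Visit 2 as baseline. Unless an unscheduled sample is taken, the baseline is therefore the value screened by exclusions [27] and [28].

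The documents give no ULN, so the following are assumptions:

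- ALT ULN 30 to 45 U/L: 99/30 = 3.30, 99/40 = 2.48, 99/45 = 2.20. At a ULN below 99/3 = 33 U/L, an unchanged 99 U/L already exceeds 3 times ULN.
- 99 U/L is the ceiling only if *and* in exclusion [27] is read as *or*. Read literally, ALT 150 with AST 60 U/L is not excluded, and 150/30 = 5.0, 150/45 = 3.3.
- Bilirubin ULN 1.0 to 1.5 mg/dL: 1.49/1.0 = 1.49, 1.49/1.5 = 0.99. An admitted 1.49 exceeds 2 times ULN only if ULN is below 1.49/2 = 0.745 mg/dL. The raised-baseline gap is therefore small for bilirubin.

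**Whether mean change fills the gap.** SAP 6.2 sets the safety endpoint as the last non-missing value up to Visit 7. For patients who taper and attend Visit 7, that value follows the taper week. For those who stop without tapering it is the early-discontinuation sample (Attachment 1, notes a and f). A peak on treatment that has resolved by then does not enter.

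Even a persisting peak is averaged away. One patient going from 1.5 to 9 times ULN among 143, others unchanged, moves the arm mean by 7.5/143 = 0.052 times ULN, or 1.6 to 2.4 U/L at ULN 30 to 45.

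**What a count could show.** The documents give no event rate, so only precision can be stated. Exact (Clopper-Pearson) 95% intervals at 143 per arm:

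| Cases | Percentage | 95% CI |
|---|---|---|
| 0 | 0 | 0 to 2.5% |
| 1 | 0.7% | 0.0 to 3.8% |
| 3 | 2.1% | 0.4 to 6.0% |
| 6 | 4.2% | 1.6 to 8.9% |

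The zero-case limit is 1 − 0.025^(1/143) = 2.5%. Two-sided Fisher tests against 0 of 143 give p = 0.060 for 5 cases and p = 0.030 for 6. Such a table can describe the arms but can hardly test them.

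The plan states no figure of its own on this point. Only the planned 143 per arm is used here.

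**The case against.** The case for leaving the plan alone is substantial.

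- **Other tables catch cases.** The protocol's adverse event definition covers abnormal laboratory findings. SAP 6.13.2 states: "The incidence of patients with TEAEs by maximum severity will be summarized by treatment group using MedDRA Preferred Term nested within System Organ Class". Protocol 8.3.3 provides for the situation "If the investigator decides that the patient should be withdrawn because of an SAE or a clinically significant laboratory value", and such withdrawals reach the tables in SAP 6.4 and 6.13.2. This stands in part. These routes depend on investigator reporting and grade clinical severity, not multiples of ULN.
- **Threshold cases are visible to the sponsor.** Under Protocol 10.4.3 the investigator consults the sponsor, and Attachment 3 tests are collected centrally. That protects the patient, but it yields no by-arm count.
- **The listing holds every value, and exploratory analyses are allowed.** This is true, and no data are lost. What is missing is a pre-specified choice of thresholds and of how to treat raised baselines.
- **The multiples are management prompts, not endpoints.** This is also true. Under 8.3.2 stopping is to be considered after consultation; it is not mandatory. Nothing in the documents requires a table by multiple of ULN.
- **Counts will be small.** This is agreed, and it is why the table should carry no test.

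A reader might go further and infer that the plan would hide liver injury, or that the SAP contradicts the protocol. The documents support neither. The values are listed, several tables would show reported cases, and the protocol's safety analysis section promises no such count.

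**Conclusion.** The point holds as an omission. The planned laboratory tables give no by-arm count of the size of an ALT, AST or bilirubin rise, or of ALT/AST elevation together with bilirubin. Their definitions also cannot register worsening from an ALT or AST baseline already above ULN. These conclusions follow from the wording of SAP 6.13.4 and need no assumed figure.

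How far above ULN a patient may start does depend on assumptions: the ULN, and how exclusion [27] is read. How many patients are affected cannot be estimated from the documents.

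The importance is modest. The change lies between optional and advisable: it improves safety reporting cheaply and leaves the primary analysis, the sample size and the monitoring rules as they are.

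**What to change.** Add to SAP 6.13.4 one by-arm table, labelled descriptive, on the safety analysis set. It should cover the treatment and tapering periods and include early-discontinuation and unscheduled samples.

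- **Shift table**, baseline category by maximum post-baseline category. For ALT and for AST: up to 1, above 1 to 3, above 3 to 5, above 5 to 8, and above 8 times ULN. For total bilirubin: up to 1, above 1 to 2, and above 2 times ULN. Count every patient with values whatever the baseline, so that everyone passing one of these multiples appears.
- **Joint row**: ALT or AST above 3 times ULN with total bilirubin above 2 times ULN, flagging same-sample cases.
- **Relative rise**: for ALT/AST baselines above ULN, the number whose maximum is at least 1.5 times and at least 2 times baseline. At an assumed ULN of 30 U/L, a rise from 99 to 149 U/L stays in one category (3.30 to 149/30 = 4.97 times ULN), but 149/99 = 1.51 meets the 1.5-times count.
- **Case listing** for each patient above 3 times ULN: dated liver values, duration above 5 times ULN, prothrombin time and eosinophils where available, and symptoms from the adverse event data.

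Keep the planned high/low table and the ANCOVA. Exact intervals may accompany the percentages.

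The cost is SAP wording, one table and one short listing that needs a merge with adverse event data. No visits, samples or staff are added. The drawback is an extra table of small counts that could be over-read, hence the descriptive label.

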6.13.5. C-SSRS Analyses

Suicide-related thoughts and behaviors based on the Columbia-Suicide Severity Rating Scale (C-SSRS) will be listed and summarized by treatment group. In particular, for each of the following suicide-related events, the number and percent of patients with the event will be enumerated by treatment: completed suicide, nonfatal suicide attempt, interrupted attempt, aborted attempt, preparatory acts or behavior, active suicidal ideation with specific plan and intent, active suicidal ideation with some intent to act without specific plan, active suicidal ideation with any methods (not plan) without intent to act, nonspecific active suicidal thoughts, and wish to be dead.

6.13.6. Falls Analyses

Numbers and percentages of patients with any falls will be summarized by treatment group and visit.

By-patient listing of fall questionnaire will be presented for the all randomized patients.

